## **4.2 Imaging and Localization Requirements**

- 4.2.1 Patient immobilization will be performed under the supervision of the treating radiation oncologist to allow for a daily reproducible setup individualized for all study subjects.
- 4.2.2 Radiation therapy treatment planning CT scans will be required to define normal patient anatomy and target volumes. The treatment planning CT scan should be acquired with each subject in the same position and using the same immobilization device as will be used for treatment. The treatment planning CT scan, however, will be performed without the use of a scrotal shielding device in place so that the CT image quality is unaltered. Treatment planning will be done using a 3D-based CT treatment planning system. The treatment planning CT scan must provide images and encompass all tissues to be irradiated, with a slice thickness of  $\leq 0.5$  cm. Images will be acquired from the top of the T8 vertebral body cranially to the mid femurs caudally. Patients being treated to the pelvic region should undergo their treatment planning CT scans and daily treatments with a full bladder (optional). These patients may be instructed to drink 16-32 ounces of fluid 30-60 minutes prior to simulation and treatment.
- 4.2.3 All patients will receive radiation therapy to the para-aortic region to allow for coverage of radiation dose to the para-aortic lymph nodes, as this nodal region is the most likely site of microscopic disease and tumor recurrence among patients with early-stage seminoma. At the discretion of the treating radiation oncologist, patients may also be treated to the ipsilateral pelvic region to allow for coverage with radiation dose to the common iliac and internal iliac lymph nodes, as this nodal region is also a known site of disease recurrence in this patient population. For patients with Stage IIA and IIB disease, the target volume *must* include the para-aortic lymph nodes and the ipsilateral pelvic region.
- 4.2.4 Contrast: Intravenous contrast may be administered during simulation at the discretion of the treating radiation oncologist to better define patient vasculature and anatomy. If intravenous contrast is used, for treatment planning purposes, a non-contrast treatment planning CT scan prior to contrast administration should be obtained. Thereafter, contrast may be administered, and the subsequent CT simulation image set may be acquired.

#### **4.3 Target Contouring and Planning**

- 4.3.1 Gross Tumor Volume (GTVnodal), defined as known measurable nodal disease, will only be employed in this study for patients with Stage IIA or IIB disease. For patients with Stage IIA or IIB seminoma, the GTVnodal will encompass nodal disease as delineated on abdominal pelvic CT.
- 4.3.2 The Clinical Target Volume (CTV), defined as the region of potential microscopic disease, will include the lymph nodes that drain the involved site(s) of interest, the corresponding vessels, and adjacent perinodal soft tissue. CTVpara-aortic and CTVpelvis will be delineated by the treating radiation oncologist as follows:
  - CTVpara-aortic
    - CTVpara-aortic includes relevant lymph node groups (interaorto-caval, precaval, pre-aortic, paracaval, and para-aortic) that drain the involved site (estimated using vascular structures of the aorta and inferior vena cava) and adjacent perinodal soft tissue.
    - Cranial border: contouring of nodal and perinodal soft tissues should terminate caudally to the T10-T11 intervertebral space to allow for adequate coverage of the retrocrural lymph nodes.
    - Caudal border: contouring of nodal and perinodal soft tissues should terminate at the level of the bifurcation of the aorta into the right and left common iliac arteries. If this bifurcation occurs cranial to the L5-S1 intervertebral space, at the discretion of the treating physician, based on contouring of the right and left common iliac vessels, the CTVpara-aortic caudal border can be extended caudally to the L5-S1 intervertebral space.
    - Left renal hilum: for patients with left-sided tumors, CTVpara-aortic also should include the branch point from where the left renal vein originates from the inferior vena cava, with contouring extending distally from this branch point to a maximum of 8 cm along the course of the left renal vein, so that CTVpara-aortic extends into the left renal hilum.
    - CTVpara-aortic is defined as the defined vessels + 1.0-1.5 cm [posteriorly, laterally, superiorly, inferiorly] and 1.5-2.0 cm [anteriorly] (for a total depth of approximately 3.0-3.5 cm anterior to the vertebral bodies) to account for perinodal tissues.
  - CTVpara-aortic + pelvis
    - CTVpelvis includes relevant lymph node groups that drain the involved site (estimated using vascular structures of the internal iliacs, external iliacs, and common iliacs) and adjacent perinodal soft tissue. CTVpelvis is defined as the defined vessels + 1.0 cm [anteriorly, posteriorly, laterally, superiorly, inferiorly] to account for perinodal tissues.
    - CTVpara-aortic + pelvis also includes interaorto-caval, precaval, pre-aortic, paracaval, para-aortic, and right and left common iliac lymph node groups, such that CTVpara-aortic + pelvis is one contiguous structure that encompasses CTVpara-aortic, so as to avoid treatment overlap of the two regions being targeted.
    - Cranial border: contouring of nodal tissues should terminate caudally to the T10-T11 intervertebral space, as per the cranial border of the CTVpara-aortic field.
    - Caudal border: contouring of inguinal nodal tissues should terminate at the obturator foramen. At the discretion of the treating radiation oncologist, the caudal border may be raised more cranially, such that contouring of inguinal nodal tissue may be excluded and contouring of external iliac nodal tissues may terminate when the iliac vessels course over the pubic symphysis or at the top of the femoral heads (a boney landmark for the inguinal ligament).
  - CTVnodal

- The CTVnodal volume is defined as GTV+ 0.2-0.5 cm [anteriorly, posteriorly, laterally, superiorly, inferiorly], with the variable margin added dependent on physician discretion.
- CTV Exclusions
  - Bone, intraperitoneal small bowel, large bowel, pancreas, and other normal adjacent structures outlined in protocol section 4.4 should be excluded from each CTV volume being targeted.
  - CTVpelvis should not extend outside of the true pelvis.
- CTVnodal should not extend outside the CTVpara-aortic or the CTVpelvis
  - Planning Target Volume (PTV) Review
    - A review volume called an PTV will be created in order to facilitate the coverage evaluation process. PTV is defined as CTV + 0.3-1.0 cm [anteriorly, posteriorly, laterally, superiorly, inferiorly], with the variable margin added dependent on range uncertainties and setup error.
- 4.3.3. Treatment Planning: After delineating the CTV, margins are added to the CTV by means of enlarging the beam aperture both laterally and cephalo-caudally in the beam's eye view, and the distal and proximal margins are calculated and added. These margins cover the uncertainty due to range, set-up errors, and lateral fall off of the irradiation fields. A compensator is created to control the dose deposition distally. Smearing and border smoothing will be routinely calculated and applied. Compensator editing may be necessary to deliver the dose as prescribed by the physician. All the above parameters are calculated and recorded by the treatment planner under physicist supervision and are subject to discussion with the treating physician, as appropriate. All these parameters can be altered by the radiation oncology team, as appropriate, in order to deliver the prescribed dose and maintain paring of the organs at risk (OAR).
- 4.3.4 Conventional photon radiation therapy backup plans may be devised. The prescription for such plans is as specified above and administered using the same scheme. The planning target volume expansion margins will be defined on case-by-case basis from the CTV volumes. The lateral margins will be defined by the multileaf collimator and will also be defined on a case-by-case basis.

#### 4.4 Normal Structures

- 4.4.1 Bilateral kidneys – will be outlined on every slice. The left renal hilum will be outlined at the discretion of the treating radiation oncologist for cases in which patients have left-sided primary tumors.
- 4.4.2 Bladder – will be outlined on every slice, including the portion inferior to the planning target volume.
- 4.4.3 Large Bowel – large bowel will be outlined on every slice as individual loops of bowel, including the portion inferior to the planning target volume.
- 4.4.4 Small Bowel – small bowel will be outlined on every slice as a compartment of potential space in which the small bowel may occupy, including the portion superior and inferior to the planning target volume.
- 4.4.5 Rectum – will be outlined on every slice, including the portion inferior to the planning target volume.
- 4.4.6 Stomach – will be outlined on every slice, including the portion superior to the planning target volume.
- 4.4.7 Pancreas – will be outlined on every slice, including the portion superior to the planning target volume.

- 4.4.8 Contralateral testicle – when possible, will be outlined on every slice, including the portion inferior to the planning target volume.
- 4.4.9 Normal Tissue Constraints
  - The mean dose to the bilateral kidneys should be  $\leq 18$  Gy (RBE).
  - The maximum dose to the spinal cord should be  $\leq 36$  Gy (RBE).
  - The maximum dose to the small bowel should be  $\leq 45$  Gy (RBE).
- 4.4.10 As neutron contamination can result in the delivery of radiation dose to the contralateral uninvolved testicle, at the discretion of the treating radiation oncologist, study subjects may be offered the use of a scrotal shielding clamshell-type device for each treatment fraction to reduce the scatter dose of radiation to the contralateral uninvolved testicle.

#### **4.5 Treatment Duration**

Proton radiation therapy will be delivered over 10 to 20 treatment days and in most instances be completed within 2.0 to 4.0 weeks from the start of treatment. This may be extended if subjects require a break from treatment. Criteria for a treatment break would include any non-hematologic Grade  $\geq 3$  toxicity.

#### **4.6 External Beam Equipment and Beam Delivery**

Treatments will be administered at the University of Pennsylvania Roberts Proton Facility and The Francis H. Burr Proton Beam Therapy Center at Massachusetts General Hospital.

#### **4.7 Quality Assurance**

- 4.7.1. Daily portal films or daily online radiographic imaging will be performed during radiation therapy. The position of the bony landmarks will be compared with DRRs (digitally reconstructed radiographs). Weekly port films will be taken for all patients.
- 4.7.2. Coronal, transverse, and sagittal CT slices with overlaid dose representing the total dose to be delivered should be available.
- 4.7.3. Dose volume histograms (DVH) will be available.
- 4.7.4. A multilevel Physics Check will be performed based on departmental protocol from the time of the simulation to treatment and will include: imaging data integrity, dose calculation accuracy, compensator check, MU calculation, and electronic records accuracy.

#### **4.8 Proton planning**

- 4.8.1 For proton planning, either posterior (PA), posterior oblique, or anterior-posterior (AP-PA) field arrangements are acceptable. The minimum number of beams necessary to meet the required treatment parameters should be used.
- 4.8.2 Uniform dose distribution by means of passive double scattering, pencil beam, spot scanning, uniform scanning, intensity-modulated proton therapy, or other delivery methods are acceptable.
- 4.8.3 Aperture, distal, proximal margin, smearing and smoothing will be determined for each case and recorded under physicist supervision.

## 5 Chemotherapy

### 5.1 Chemotherapy as Primary Therapy

No chemotherapy is to be administered in the adjuvant setting during the primary protocol study treatment period.

### 5.2 Chemotherapy as Salvage Therapy

If a patient is found to have clinical or radiographic evidence of disease recurrence or a worrisome radiographic abnormality, pathological assessment is strongly encouraged, but not required, to confirm disease recurrence. The pathological confirmation of disease recurrence at any site or the initiation of salvage therapy will be considered a failure of protocol treatment, and such patients will be removed from study and followed for late effects and survival. Subsequent management and salvage therapy of patients who have failed protocol treatment will be left to the discretion of the treating oncologist, with the treatment modality and treatment regimen dictated by the location and extent of tumor recurrence at the time of evaluation.

## 6 Study Procedures

This study will be performed jointly at the University of Pennsylvania and Massachusetts General Hospital (MGH). The coordinating center will be the University of Pennsylvania. When a patient is being evaluated for this study, the study coordinator from Massachusetts General Hospital will contact the study coordinator at Penn to determine if an enrollment slot for this study is available. The study coordinator from the DOD will call the coordinating center to refer the patient and schedule an appointment with a physician. At the time of study enrollment and determination of eligibility, the study coordinator from MGH will contact the study coordinator at Penn to reaffirm that a slot is available. The study coordinators at Penn and MGH will have a formal teleconference monthly (or as needed) to discuss study progress and current toxicities. At any time a grade 3 toxicity has been observed, communication between the study clinicians will take place within 5 business days. A formal teleconference including the study coordinators and PIs at Penn and MGH will take place on a monthly basis (or as needed) to review study progress. The decision to proceed from one dose level to the next will be made at the time of a formal PI and study coordinator teleconference.

### 6.1 Study Parameters Table

Eligibility/ Pre-Treatment	Weekly During Radiation Therapy	Weekly for 8 Weeks Following Radiation	90 Days From the Start of Treatment	Q6 Months for Year 2 Post Treatment	Q12 Months for Years 3-5 Post Treatment
-------------------------------	--	---	--	--	--

		Treatment	Therapy Completion	nt and Then Q3 Months for Year 1 Post Treatment		(Approx.)
History and Physical Examination	X	X***		X	X	X
Performance Status Assessment	X	X		X	X	X
EORTC QLQ-C30*	X	X	X 	X 	X 	X 
Testicular Cancer Patient Diary Card*	X	X	X 			
EuroQol EQ5D*	X	X	X 	X 	X 	X 
Chest X-ray or CT Chest	X 			X	X	X
Abd/ Pelvic CT Scan or Abd/Pelvis MRI	X  (abdominal and pelvic CT scan)			X (once annually; not required for patients receiving pelvic radiation therapy)	X (once annually; not required for patients receiving pelvic radiation therapy)	X (once for year three; not required for patients receiving pelvic radiation therapy)
MRI Brain and/or Bone Scan	X (if clinically indicated)					
Toxicity Assessment	X	X		X	X	X

Eligibility/ Pre-Treatment	Weekly During Radiation Therapy Treatment	Weekly for 8 Weeks Following Radiation Therapy Completion	90 Days From the Start of Treatment and Then Q3 Months for Year 1 Post	Q6 Months for Year 2 Post Treatment	Q12 Months for Years 3-5 Post Treatment
----------------------------	---	---	--	-------------------------------------	---

			Treatment		
Semen Analysis (recommended, but not required)	X 		X (at one year only)		
Complete Blood Count	X 	X 	X	X	X
Follicle-stimulating Hormone and Luteinizing Hormone	X 				
Lactate Dehydrogenase	X 		X	X	X
Human Chorionic Gonadotropin	X 		X	X	X
Alpha-fetoprotein	X 		X	X	X
testosterone	X 		X 	X 	X 

Follow up visits may be scheduled +/- 4 weeks

\* All procedures **not** marked with "\*" are standard of care procedures.

\*\*\*During weekly treatment, a pertinent physical exam may be performed

 Forms may be obtained 1 day prior or 3 days post treatment

 Forms may be obtained +/- 1 week

 Forms may be obtained +/- 2 weeks

 Forms may be obtained +/- 1 month

 Must be obtained before radiation treatment begins. If these values are available pre-operatively, they will be recorded.

 Must be performed approximately within 6 weeks of study

 Testosterone assessment is required only at pre-treatment, 6 month, 2 year, and 5 year follow up visits.

 Complete Blood Count (CBC)- this lab will be optional, weekly during treatment.

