# 1 Introduction

## 1.1 Background

Testicular cancers are the most common solid malignancies among men aged 20 to 35 years, with a projected 8,400 new cases of testicular malignancies in the United States annually (1). Approximately 60% of these malignancies represent pure seminomas, and 80% of patients diagnosed with seminoma have stage I disease (2-3). The standard initial treatment for stage I seminoma is radical inguinal orchietomy. Photon external beam radiation therapy has been standard adjuvant treatment and can achieve cause-specific survival rates approaching 100% and long-term relapse-free survival rates in excess of 95%, with virtually no relapses within the radiation portal (4-8).

However, radiation-induced treatment morbidities for seminoma have been reported. Acute toxicities are generally mild and self-limiting and include fatigue and gastrointestinal symptoms. Patients, however, are at an increased risk of late gonadal toxicity (9-11) and cardiovascular disease (12-14). Cardiac risks are higher among patients treated with mediastinal radiotherapy when compared to those treated with infradiaphragmatic radiation alone (12), patients receiving chemotherapy in addition to radiation therapy, and smokers (13, 15).

Following adjuvant radiation therapy, patients with seminoma are also at increased risks of contralateral testicular germ cell tumors in the first decade following adjuvant radiation therapy (16-18) and non-germ cell solid malignancies (RR = 2.0, 95% CI = 1.9-2.2) 10 to 35 years following radiation therapy (12-13, 15, 18-24). The risk of solid malignancies is higher for patients diagnosed with testicular cancers at younger ages. Based on tumor registry data, a patient diagnosed with a seminoma at age 35 years has a 36% risk of developing a second solid cancer within 40 years of his diagnosis, compared with 23% for the general population. As seminoma largely affects younger patients, and the cure rates from standard therapy are excellent, second primary cancers have emerged as a leading cause of death among survivors of testicular malignancies (12-13, 24).

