## 4 Radiation Therapy

### 4.1 Dose fractionation and specification

- 4.1.1 For patients with Stage I Seminoma, radiation fractions will be administered once daily, for five fractions per week from Mondays through Fridays, as well as weekends when deemed clinically appropriate, with the exclusion of Hospital Holidays, for a planned 10 to 25 fractions delivered over two to four weeks. For patients with Stage IIA and IIB Seminoma, an additional boost of 5 fractions will be delivered over 5 days. The number of fractions administered will be dependent of the clinical stage of each study subject.
- 4.1.2 For Stage I Seminoma, patients will be treated to a total dose of 20.0 Gy (RBE) to 30.0 Gy (RBE) in 150 cGy (RBE) to 200 cGy (RBE) fractions to CTVpara-aortic for those being treated to

the para-aortic region alone or to CTVpara-aortic + pelvis for those being treated both to the para-aortic and pelvic regions. For patients with Stage IIA and IIB Seminoma, the target volume must include the both the para-aortic and pelvic regions and a nodal volume encompassing nodal disease (prescribed to an additional 9.0 Gy (RBE) to 10.0 Gy (RBE) in 180 cGy (RBE) to 200 cGy (RBE) fractions. The treatment field and total radiation dose will be at the discretion of the treating radiation oncologist, and dependent on the clinical risk factors of each study subject. The maximum dose should not exceed the prescription dose by more than 7% (inhomogeneity less than or equal to 7% in a volume of 1 cc of the review structures).

- 4.1.3 Treatment breaks, if necessary, should not exceed two treatment days. Treatment breaks exceeding two days will be considered a major protocol violation. Treatment breaks should only be allowed as a means for study participants to recover from severe acute toxicity and/or for intercurrent illness, or due to treatment machine or cyclotron maintenance. To avoid treatment breaks, a photon-based backup treatment plan may be delivered. Any treatment break or delay for other social or logistical reasons will be considered a protocol deviation. Photon-based backup treatment should not exceed 2 days or 10% of the intended dose of radiation, whichever is less. All incidents of treatment breaks and the reasons for any such breaks must be clearly indicated in the treatment record.

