6.2.7 Years 1-5 Post Treatment: each patient will be assessed 90 days following the start of radiation therapy and then every three months for one year, every six months during the second year following therapy, and annual for years three to five or longer following therapy. Each follow-up assessment will include an interval history and physical examination, performance status assessment (Appendix C), toxicity assessment (as per protocol section 6.2.5), quality of life assessment with EORTC QLQ-C30 (Appendix D) and EuroQol EQ-5D (Appendix F), and laboratory evaluation with serum creatinine and/or creatinine clearance, complete blood count, testosterone (at specified timepoints), lactate dehydrogenase, human chorionic gonadotropin, and alpha-fetoprotein. Additionally, semen analysis will be obtained 12 months following the completion of therapy. A chest x-ray or CT Chest will be obtained at each patient follow-up visit during years one through five following the completion of therapy. In patients with continued follow-up beyond five years, chest x-rays or CT Chest thereafter will be performed at the discretion of the evaluating physician. For patients not receiving pelvic radiation therapy, follow-up assessments will include a CT abd/pelvis or MRI abd/pelvis scan annually for the first three years following the completion of therapy.

- Toxicity assessment from years five through 15 will include inquires of any renal disease, cardiac disease, and second malignancies that the study participants may have been diagnosed with since the completion of the primary protocol study treatment period. If a patient has been

diagnosed with a second malignancy, details of the disease primary location, histology, staging, treatment regimen received, and disease status should be obtained. Copies of pertinent pathology reports, imaging reports, and treatment details should also be obtained.

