#### 7.1.4 Statistical Analyses.

- Acute and Late Toxicity: All acute and late toxicities will be graded by CTC Version 4.0 and tabulated. Toxicity rates and 95% confidence intervals will be calculated.
- Analysis by Radiation Therapy Type: all subjects enrolled in this study will be followed and assessed for all endpoint analyses. However, a separate analysis may be performed for subjects who were treated with photon therapy as a portion of their planned course of radiation therapy.
- Moderate to Severe Lethargy: The 3-week rate and 95% CI will be computed. A one-sample one-sided chi-square test will be performed to test the null hypothesis that the lethargy rate is 35% (same as photon) versus the alternative hypothesis that the rate is reduced to 20%. Patients must have a minimum of 21 days of follow-up to be included. As a secondary analysis, the 3-week lethargy rate and 95% exact CI will be computed for each disease stage. A Fisher's exact test will be employed compare these rates, to determine whether lethargy rates significantly differ by disease stage.
- Clinical Efficacy: Time to local failure and time to distant failure will be estimated by the cumulative incidence method within a competing risks framework (competing risks are local failure, distant failure, death). Relapse-free survival, cause-specific survival, and overall survival will be estimated by the Kaplan-Meier method. Median values and 95% confidence intervals will be calculated.
- Quality of Life: Longitudinal quality of life measurements will be examined by plots of mean $\pm$  SD over time. Repeated measures ANOVA or linear mixed effects models (to assess the impact of fixed effects covariates), will be used to analyze the repeated observations. Piecewise linear models may be required to fit non-linear trends, as expected for the initial decline and then gradual increase in quality of life measures.

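### The scan waiver for pelvic-field patients leaves every Stage II patient with no required abdominopelvic imaging after treatment, and the Stage II entries in the schema, 3.2.1 and Appendix B do not agree

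*Combined protocol and SAP*

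**What the plan says.** **Imaging.** The table in 6.1 lists follow-up abdominal/pelvic CT or MRI in years 1 and 2 as "once annually; not required for patients receiving pelvic radiation therapy", and once in year 3 with the same waiver. Section 6.2.7 puts it the other way round: "For patients not receiving pelvic radiation therapy, follow-up assessments will include a CT abd/pelvis or MRI abd/pelvis scan annually" for three years. Neither place separates patients by stage. Chest imaging is handled differently: "A chest x-ray or CT Chest will be obtained at each patient follow-up visit during years one through five".

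**Fields.** For Stage IIA/IIB, 4.1.2 says that "the target volume must include the both the para-aortic and pelvic regions". Section 4.2.3 repeats that the volume has to "include the para-aortic lymph nodes and the ipsilateral pelvic region". For Stage I the pelvic field is left to the treating radiation oncologist.

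**Failure and its analysis.** Under 5.2, "The pathological confirmation of disease recurrence at any site or the initiation of salvage therapy will be considered a failure of protocol treatment". Section 2.3.1 asks for the efficacy outcomes by clinical stage and by target volume. Section 7.1.4 states that "Time to local failure and time to distant failure will be estimated by the cumulative incidence method within a competing risks framework", with Kaplan-Meier estimates for relapse-free survival. It plans no between-group efficacy test.

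**Staging.** Section 3.2.1 admits Stage II as N1 or N2 with S0-3 and cites Appendix B. The two Stage II rows of Appendix B both read N1, M0, S0-S1. The schema's patient list excludes N1 and N2, yet also admits IIA and IIB with nodal disease on CT, and it refers the reader to 3.2 and 3.3 for eligibility.

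**The concern.** The waiver is attached to the radiation field. Because Stage II patients must have that field, the waiver reaches all of them. They are the only patients with measurable nodal disease (4.3.1), and under 4.3.2 their nodal volume must stay inside the para-aortic and pelvic targets. The region in which a local failure would arise is therefore the region with no scheduled scan.

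The reasons given do not extend to this group. Section 1.1 ties annual pelvic CT for three years to Stage I patients treated to the para-aortic region alone. Section 1.2 argues that adding a pelvic field in Stage I removes the need for pelvic CT. Neither explains omitting abdominal as well as pelvic imaging after treatment of gross nodal disease.

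What is at stake is the date of failure. Section 5.2 counts failure at pathological confirmation or start of salvage, after clinical or radiographic evidence has prompted a work-up. For a clinically silent abdominopelvic relapse in a Stage II patient, that date depends on whether and when a clinician orders an unscheduled scan.

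The staging entries raise a separate issue of who is eligible and how patients are grouped. The grouping is used for the by-stage efficacy summaries and for the Fisher's exact test of lethargy by disease stage in 7.1.4. Section 9.2.2 in general allows no exceptions from the eligibility criteria, so those criteria need to read one way.

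**Working it through.** The plan states no figure on this point, so the check is a count from its own rules plus a bound on the size of the effect.

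**1. Required post-treatment abdominopelvic scans per patient (6.1, 6.2.7, with 4.1.2 and 4.2.3)**

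| Group | Year 1 | Year 2 | Year 3 | Total |
|---|---|---|---|---|
| Stage I, para-aortic only | 1 | 1 | 1 | 3 |
| Stage I, pelvic field | 0 | 0 | 0 | 0 |
| Stage IIA/IIB (pelvic field compulsory) | 0 | 0 | 0 | 0 |

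**2. Required chest imaging, for comparison.** Reading 6.2.7 as visits at months 3, 6, 9 and 12, two in year 2, and one in each of years 3 to 5: 4 + 2 + 3 = 9 for every patient.

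**3. How many events could be affected.** The number of Stage II patients is not given. Assume 10%, 20% or 30% of 56:

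- 0.10 × 56 = 5.6, about 6
- 0.20 × 56 = 11.2, about 11
- 0.30 × 56 = 16.8, about 17

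The end of section 1.2 gives five-year disease-free survival of 90% or higher for IIA and nonbulky IIB, so at most 10% are expected to have an event. Expected events are at most 0.10 × 6 = 0.6, 0.10 × 11 = 1.1 and 0.10 × 17 = 1.7. These cover all sites and all modes of detection. Only clinically silent abdominopelvic relapses are exposed to the gap, so the affected number is smaller still. This is an expected count, not a limit on what may be observed, and it rests on that survival figure carrying over to this trial.

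**4. Scans added by the fix.** Three per Stage II patient: 3 × 6 = 18, 3 × 11 = 33, 3 × 17 = 51.

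**5. Staging entries side by side (Stage II)**

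| Place | N | S |
|---|---|---|
| Schema | N1 and N2 excluded, but IIA/IIB with nodal disease admitted | none given |
| 3.2.1 | N1, N2 | S0-3 |
| Appendix B, IIA row | N1 | S0-S1 |
| Appendix B, IIB row | N1 | S0-S1 |

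The N definitions earlier in Appendix B separate N1 (up to 2 cm) from N2 (over 2 cm, up to 5 cm), so the identical IIB row is a typing error. The S mismatch is not explained that way: a Stage II patient with S2 or S3 meets 3.2.1 but falls in neither Appendix B row. Stage I has no such conflict, because Appendix B includes Stage IS with S1-S3.

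**The case against.** The strongest reply is that the waiver may be deliberate and matters little.

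- Not requiring a scan does not forbid it. Section 6.1 treats unstarred procedures, this one included, as standard of care. Examination, LDH, hCG, AFP and chest imaging continue for everyone. This stands: Stage II patients may well be scanned, and the rate is unknown. A reader might infer that they go without relapse surveillance; the documents do not say so. What is missing is a common schedule.
- Concern about cancers induced by surveillance CT runs through sections 1.1 and 1.2, and 1.1 reports "virtually no relapses within the radiation portal". That statement is about adjuvant photon treatment of Stage I. It does not settle the matter for gross nodal disease.
- The affected endpoints are secondary and descriptive, and few events are expected. This stands and limits the weight of the point.
- The three-year annual schedule is borrowed from para-aortic-only Stage I, and applying it to Stage II splits the pelvic-field group into patients with 3 scans and patients with 0. Both are true. The split is why imaging frequency must be shown with the by-volume estimates.
- Annual scans may seem to guarantee detection within about a year. They do not. One scan in each year is satisfied by month 3 and month 24, which are 24 − 3 = 21 months apart, and nobody has a required scan after year 3.
- The schema defers to 3.2 and 3.3, and the IIB cell is clerical. Both are fair. Nor is there a three-way conflict on S, since the schema gives no S category. The S0-3 entry in 3.2.1 remains inconsistent with the appendix it cites.

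**Conclusion.** The point holds as a modest one that should be corrected. By the plan's own rules, Stage II patients have 0 required abdominopelvic scans after treatment, and the stated rationale does not cover them. Failure dates in the by-stage local failure and relapse-free survival estimates therefore rest partly on unscheduled scanning.

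The effect is probably small: at most about 0.6 to 1.7 expected Stage II events, assuming 6 to 17 such patients and five-year disease-free survival of at least 90%. Bulky IIB, which 3.2.1 lets the investigators exclude but does not bar, may not fit that figure. The bias in the estimates cannot be computed, because the Stage II share, relapse sites and unscheduled scanning rate are not given.

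A reader might infer that the trial's main conclusion is at risk. It is not: the overall 3-week lethargy test, toxicity, quality of life and overall survival do not depend on these scans. Nor do the documents show that any patient was wrongly enrolled or staged.

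On staging, the S0-3 entry for Stage II and the schema's exclusion of N1 and N2 are wrong as written; the Appendix B IIB row is a typing error.

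**What to change.** 1. In 6.1 and 6.2.7, limit the scan waiver to Stage I patients given a pelvic field. Stage II then follows the existing annual schedule in years 1 to 3, with MRI allowed.
2. Record the date of every abdominopelvic scan, scheduled or not. Show imaging frequency beside the by-stage and by-volume estimates, since Stage I pelvic-field patients will still have no required scan.
3. In 3.2.1, restrict Stage II to S0-S1 to match Appendix B.
4. Delete N1 and N2 from the schema's exclusion and keep the exclusion of M1.
5. Correct the Appendix B IIB row to N2.

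The cost is one amendment and a case report form field for scan dates. Up to three scans per Stage II patient become required: 18, 33 or 51 in all on the assumed shares of 10%, 20% or 30%. That adds some CT exposure where MRI is not used, although 6.1 already classes the scan as standard of care. Imaging within the pelvic-field group becomes mixed, which item 2 makes visible but does not remove.
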